### **The study aims are to:**

1. Develop our proposed preliminary computer-based intervention, incorporating information gained in informant interviews.
2. Perform a small open trial (n = 20) of SHE to assess feasibility of recruitment of target population and acceptability of intervention and study procedures.
3. Conduct an initial randomized control trial in a sample of no more than 155 women Veterans who screen positive for lifetime sexual trauma (ST) and have at least one risk factor (i.e., screen positive for intimate partner violence (IPV), posttraumatic stress

disorder (PTSD), and/or heavy drinking) to demonstrate the feasibility of SHE and the acceptability of SHE via participant report of ease of use, helpfulness, and overall satisfaction.

4. Examine preliminary evidence for the hypotheses that, relative to the control condition, screening and referral only (SR), SHE will result in:
  - Decreases in the number of risks (i.e., heavy drinking (4+ drinks on one occasion), screen positive for PTSD, screen positive for IPV) at the 2- and 4-month follow-up (*primary*).
  - Increases in resource and treatment utilization over the 2- and 4-month follow-up period (*secondary*).

The data will be used to demonstrate whether the effects of the intervention look promising to support a future large-scale randomized control trial and to suggest, in concert with results from clinical trials in related fields, the range of effect sizes that would be reasonable to expect in a future trial.

This is a multi-site study. At the Providence, RI based site (Women and Infants Hospital and Brown University), the specialized computer-based assessment and interactive intervention sessions will be developed and designed and staff members will also assist with data management. The Central Texas VA Healthcare System site will be the data collection site and the main site for participant recruiting, consenting, enrollment, intervention and follow-up. Staff at the two sites will work collaboratively throughout the project to supervise study staff, for reporting to the DOD and IRB's and in designing the assessment and intervention sessions, however, only the study staff at the Central Texas site will have access to participant PHI.

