### ***Subjects***

We will sample consecutive eligible patients from Women's Primary Care at the Waco and Temple VA medical centers. Participants will be women Veterans seeking treatment in women's primary care.. Participants must report a history of lifetime ST and have at least one of the following risks: 1) Alcohol (i.e., report exceeding the national recommended limits for daily drinking (4 or more for women) on at least one occasion in the past month); 2) PTSD (i.e., screen positive for current PTSD) and screen positive for IPV within the last 12 months. Participants who indicate one or more of these risk factors will be included in the study. Other inclusion criteria will be ability to understand study procedures in English, be between the ages of 18 and 65, and willingness to complete follow-up session. In future studies, the computer software can be modified to present information in Spanish for the Latina population.

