appointment at the women's clinic. If so, the participant will be provided with referrals, and screening will be postponed until their period of intoxication is over on the same day or rescheduled for a later date. To guarantee that the participant is not intoxicated prior at the time of screening, any participant who had either initially endorsed drinking alcohol prior to their rescheduled appointment and who did not endorse drinking alcohol on the day of their rescheduled appointment or participants who do not endorse drinking alcohol but exhibit behaviors consistent with intoxication (e.g., slurred speech, belligerence, etc...) will be administered a breath alcohol test, and must register  $<.02$  breath alcohol content. Once it is determined that the participant is not intoxicated, she will complete the 30-minute screener using the CIAS software delivered on a VA issued/ approved laptop computer or desktop computer to determine study eligibility. Participants will wear headphones to hear the audio for the computerized screening and a screen protector will be on the computer so no one could inadvertently observe the screen. The use of audio computer-assisted self-interview software to conduct screening will maximize identification rates of women Veterans with ST, IPV, alcohol misuse, and PTSD. The screener will include a brief series of questions about general health, exercise, diet, smoking, and sunscreen. The screener will also include the following well-validated, reliable and recommended measures: Participants must report a history of lifetime ST (as identified by the Sexual Experiences Survey—Short Form Victimization (SES-SFV), items from the VA MST screener, and the Childhood Sexual Victimization Questionnaire (CSVQ) and have at least one of the following risks: 1) Alcohol (i.e., report exceeding the national recommended limits for daily drinking (4 or more for women) on at least one occasion in the past three months as indicated on the Graduated Frequency Measure (GFM)); 2) PTSD (i.e., screen positive for current PTSD with a cut point of  $\geq 36$  on the PTSD Checklist for DSM-V; and IPV within the last 12 months (i.e., score 4 or more on the Woman Abuse Screening Tool (WAST)).

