**Screening measures:** As described above, the screener will include the following brief series of questions about general health and the following well-validated, reliable and recommended measures. Lifetime ST will be assessed via the SES-SFV, items from the VA MST screener, as well as the CSVQ. Specifically, the SES-SFV will assess experiences of unwanted sexual contact, sexual coercion, attempted rape and rape experienced from the age of 14 to the time of the survey. The SES-SFV is commonly utilized in research of sexual trauma, and utilizes a series of 10 behaviorally-oriented and sexually-explicit questions to assess several types of victimization experiences. Prior research with the SES-SFV suggests that versions of the scale demonstrate good test-retest reliability ( $r = .93$ ), and adequately captures the legal definitions of attempted rape and rape. The quantity and frequency of alcohol use will be assessed during the screening using the Graduated Frequency Measure (GFM). An algorithm is utilized to quickly score the measure to determine whether the participant exceeds the national recommended limits for daily drinking (4 or more for women) over the specified recall period. Symptoms of PTSD will be assessed with PTSD Checklist for DSM-5 (PCL-5). Individuals will be classified as screening positive for current PTSD if the sum score is equal to or greater than 33. The PCL-5 is considered a “best practice” instrument in the assessment of PTSD. At screening, IPV in the past year will be assessed with the Woman Abuse Screening Tool (WAST), which was originally designed for use in primary care settings, is an 8-item instrument that measures physical, sexual, and emotional abuse in the last 12 months and is consistent with the definition of IPV as defined by The American College of Obstetricians and Gynecologists. It has correctly classified 100% of nonabused women and 92% of abused women in a known-group analysis, has good internal reliability, and has adequate concurrent validity. Consistent with similar studies, IPV status is positive if a woman obtains a score of 4 or more on the WAST.

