**Baseline and follow-up measures of alcohol use:**

Participants who screen eligible for the study, and enroll will complete additional measures of alcohol use at the baseline assessment. At baseline and at follow-up, alcohol use will be assessed with the 30-day Alcohol Timeline Follow back\* (TLFB), a calendar-assisted measure used to garner a retrospective account of drinking behavior. The TLFB will be used to calculate any vs. no heavy drinking (i.e. 4 or more drinks on one occasion during the past 30 days) for primary study analyses. At each follow-up point, the TLFB will assess substance use

since the previous follow-up point. The TLFB has excellent reliability and validity for alcohol, and is sensitive to change as used in this study. The TLFB is commonly utilized to provide feedback to participants regarding the quantity and frequency of alcohol use, and provide an estimation of blood alcohol content on average and peak drinking day.

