**Baseline and follow-up assessments of IPV:** : The Composite Abuse Scale (CAS) will assess the chronicity and occurrence of violence with their current partner (over the past year). At subsequent assessments it will be administered for the time since last assessment. The CAS, a widely used self-report of behaviors, has 30 items presented in a six point format requiring respondents to answer "never", "only once", "several times", "monthly", "weekly" or "daily"-over the specified time period. The CAS has 4 subscales that measure severe, combined abuse, emotional abuse, physical abuse, and harassment. The CAS has recently been published in the Centers for Disease Control and Prevention compendium of intimate partner violence measures. The scale will be coded categorically (no violence vs. any on one or more CAS subscales of combined abuse, emotional abuse, physical abuse, and harassment) for the primary study analyses. The scale will also permit exploratory analyses of decreasing the frequency of violence among participants.

The 15-item checklist the Safety-Promoting Behavior Checklist (SPBC) will be used to assess the participant's use of strategies that could protect her from IPV in the future (e.g., hiding money and extra clothing). All questions begin with the phrase, "Have you ever . . ." followed by specific safety-promoting behaviors. In subsequent assessments the same series of questions, it will be administered for the time since last assessment. The SPBC has been used successfully in interventions for women with IPV that have like SHE targeted an increase in safety behaviors.

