**Primary outcomes (Aim 4a):** Following the intention-to-treat principle, all women who completed the baseline assessment and who are randomized will be included in the analyses. Analyses will first test the hypothesis that SHE reduces the number of risks relative to control. Quantification of post-intervention behavioral change will be estimated by comparing the distributions of the number of risks in the two groups at baseline and follow-up. Within-person changes in the number of risks over time will also be examined. Specifically, women will be characterized by the number of risks (one through 3) at baseline. That will serve as a covariate in a model predicting number of risks at 2 and 4 months, which will be analyzed using generalized estimating equations (GEE) with a Poisson distribution specified. GEE is a method of repeated measures analysis commonly utilized for binary outcomes that allows for the inclusions of both categorical and continuous independent variables, as well as appropriate modeling of covariates when observations are correlated across time. The primary between group independent variable will be program group; dummy coded using the intervention as the reference category.

To further illustrate program effects, each of the participants will then be classified over the follow-up as 1) resolving all risks; 2) resolving some but not all risks; and 3) resolving no risks or increasing the number of risks. Intervention effectiveness will be measured by comparing the proportion of women resolving all risks, to the proportion of women resolving no risks or increasing risks between the groups. The proportion of women resolving all risks will also be compared to the proportion of women resolving some risks between groups.

**Secondary outcome (Aim 4b):** Analyses will also examine comparisons between groups in the extent of change in use of treatment (TSR and CPRS number of mental health visits) and resource utilization (EOR) (secondary outcome) as well as the extent of change on individual risk factors overtime using generalized estimating equations (GEE) (i.e., occurrence of IPV as measured by the CAS, screen positive for PTSD diagnosis as measured by the cut point of  $\geq 33$  on PCL-5, heavy drinking status as measured by the TLFB).

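### The plan does not say how the baseline number of risks is scored; its range of one to three fits only the screening rules, while the follow-up alcohol and IPV risks use other instruments

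*Combined protocol and SAP*

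**What the plan says.** **Baseline count.** Under Data Analysis, Primary outcomes (Aim 4a), "women will be characterized by the number of risks (one through 3) at baseline". The count is a covariate in a Poisson GEE for the number of risks at 2 and 4 months. The same section plans to examine within-person change and to sort women into three classes: all risks resolved, some resolved, or none resolved or more risks than before. It names no instrument for the count.

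**Entry.** Under Subjects, "Participants who indicate one or more of these risk factors will be included in the study". The screener uses the GFM, the PCL-5 and the WAST. For IPV, "IPV status is positive if a woman obtains a score of 4 or more on the WAST". For alcohol, Screening and Informed Consent Procedures requires a heavy occasion "on at least one occasion in the past three months as indicated on the Graduated Frequency Measure (GFM"; Subjects says "on at least one occasion in the past month". The PCL-5 cut point is 36 under Screening and Informed Consent Procedures, but 33 under Screening measures and in Data Analysis.

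**Primary analyses.** For alcohol, "The TLFB will be used to calculate any vs. no heavy drinking", meaning four or more drinks on one occasion in the past 30 days. For IPV, "The scale will be coded categorically (no violence vs. any on one or more CAS subscales".

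**Schedule and windows.** Table 1 places GFM and WAST at screening only; TLFB and CAS at baseline, 2 and 4 months; and PCL-5 at screening, 2 and 4 months. The CAS covers the past year at baseline and the time since the last assessment afterwards. The TLFB is a 30-day calendar, but at follow-up it asks about the period since the previous follow-up point.

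**Aims.** Aim 4 lists as a risk "screen positive for IPV) at the 2- and 4-month follow-up", although the IPV screen is not repeated.

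**The concern.** The baseline count is the starting point for within-person change, for the three resolution classes and for the proportion with any reduction that the Power Analysis uses. Each of these is meaningful only if a risk is defined the same way at both ends. The stated range points to the screener, while the definitions given for the primary analyses point to the TLFB and CAS. The two differ in instrument, threshold and window, so a change in the count could reflect a change of ruler.

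This matters because the Power Analysis says that the main objective is an effect size for planning the next trial. A change-based effect size that carries false resolution or false gain would mislead that planning.

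**Working it through.** **1. Definitions side by side.**

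| Risk | Screening | Primary analyses, baseline | Primary analyses, follow-up |
|---|---|---|---|
| Alcohol | GFM, any 4+ occasion; past three months or past month, depending on section | TLFB, any 4+ occasion in 30 days | TLFB, same rule, but asked since the previous point |
| IPV | WAST of 4 or more, 12 months | CAS any vs none, past year | CAS any vs none, since last assessment |
| PTSD | PCL-5, cut 36 or 33 depending on section | not given; the screening value serves | PCL-5, cut 33 |

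**2. Two readings of the baseline count.**

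- *Screening instruments.* One to three is right, but two of the three risks change definition. A woman below 4 on the WAST who reports the same low-level abuse on the CAS at both times gains a risk. Under the three-month window, a woman whose only heavy occasion was ten weeks before entry is already negative on the 30-day TLFB rule at baseline and can later be classed as resolved.
- *Baseline TLFB and CAS.* The definitions match better, but a woman who qualified on the GFM or WAST can score zero. The stated range is then wrong. A woman going from zero to zero could be called all resolved or none resolved, and she can never show a reduction.

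**3. The plan's own figure.** Power Analysis: power .85 for any reduction, 20% control vs 40% SHE, h = .44, N = 155, alpha .05 with sidedness not stated.

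h = 2·arcsin√.40 − 2·arcsin√.20 = .442. Power = Φ(h·√(N/4) − z), and .44·√(155/4) = 2.739.

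- One-sided: Φ(2.739 − 1.645) = .863, which matches.
- Two-sided: Φ(2.739 − 1.960) = .782, which does not.
- With the 126 women the plan expects to retain: .795 one-sided, .695 two-sided.

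The stated figure is therefore reached only one-sided and without attrition. That is a separate matter, but it fixes the starting point here.

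**4. Illustration for any reduction.** Assume that a share f of women with no true reduction is classed as reduced, equally in both arms. Control becomes .20 + .80f and SHE becomes .40 + .60f. No value of f can be taken from the documents.

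| f | Control | SHE | h | Power, N = 155, one-sided | Two-sided |
|---|---|---|---|---|---|
| 0 | 20% | 40% | .442 | .866 | .786 |
| .10 | 28% | 46% | .376 | .756 | .647 |
| .20 | 36% | 52% | .324 | .645 | .522 |

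(The first row uses the unrounded h.)

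**5. Alcohol: how many could already be negative at baseline?** Assume heavy occasions follow a Poisson process at constant rate, with mean m per 90 days. Then P(none in the last 30 days, given at least one in 90) = (e^(−m/3) − e^(−m)) / (1 − e^(−m)).

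- m = 1: .55; m = 3: .33; m = 6: .13.
- At the plan's 40% alcohol-positive (62 of 155), that is about 34, 21 or 8 women.
- Under the past-month window in Subjects, the GFM and TLFB windows agree and the share from this cause is about none.

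**6. IPV: matching the instrument is not enough.** Take the plan's 25% over 4 months as a constant rate, λ = −ln(.75)/4 = .0719 per month. The chance of no event in 2 months is e^(−2λ) = .866. So 87% of women positive on the past-year CAS would be negative at 2 months with no true change. If rates vary between women (gamma-Poisson, shape 1 to 0.1, still 25% over 4 months), the share is 79% to 42%. All of this rests on assumption.

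**7. IPV: no head count.** The 40% in the Power Analysis is lifetime IPV, not WAST-positive in the past 12 months. The number of WAST-negative women, or of women gaining a CAS risk, cannot be derived from it.

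**The case against.** The best defence is that the plan already means the like-for-like count. The data-checking paragraph says analyses adjust for baseline levels of the dependent variables. Table 1 labels TLFB and CAS as primary outcomes and gives both at baseline, while GFM and WAST are labelled as screening only. PTSD, expected in 60% of women, uses the PCL-5 throughout. The resolution classes are offered only as further illustration.

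Much of this stands. A reader might infer that the baseline count is definitely taken from the screener. The documents do not say so, and the data-checking sentence points the other way. But if the defence is right, one to three cannot be the range, the classes have no place for zero, and the CAS window still changes between baseline and follow-up.

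A reader might also infer that the primary treatment comparison is biased or diluted. That is not supported. The dependent variable is the follow-up count, scored alike in both arms, and the baseline count enters only as a covariate. Rescoring it leaves the outcome unchanged.

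Nor do the documents show that a woman negative on the WAST but positive on the CAS would miss the IPV module. Modules follow her risk profile, the WAST is not named as the rule for assigning them, and IPV feedback within the module uses the CAS.

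**Conclusion.** The point holds as a gap in the definition of a key variable. Either the baseline and follow-up counts are not like for like, or the stated range and the three classes are wrong. The harm falls on within-person change, the resolution classes, the any-reduction proportion and effect sizes taken from them. It does not fall on the GEE comparison of follow-up counts by arm.

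The size is illustrative. With 10–20% false reductions assumed in both arms, h for any reduction falls from .44 to .38–.32. The share of alcohol-positive women already TLFB-negative at baseline runs from about none (past-month entry) to 13–55% (three-month entry, constant-rate Poisson). No IPV count can be given.

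**What to change.** - State the instrument, threshold and recall window for each risk at baseline, 2 and 4 months.
- Define the baseline count by the follow-up rules: TLFB any 4+ occasion in the past 30 days at every visit, CAS any vs none, and the screening PCL-5 at the Data Analysis cut point of 33. Let it range from 0 to 3.
- Keep GFM and WAST for eligibility.
- Keep women with a baseline count of 0 in the GEE, but report them separately from the resolution classes.
- Align the CAS windows. Otherwise do not interpret baseline-to-follow-up CAS change as resolution, and rely on the between-arm comparison at follow-up.
- Reword Aim 4 so that IPV at follow-up is CAS-defined.
- Reconcile the two alcohol entry windows (Subjects vs Screening and Informed Consent Procedures) and the two PCL-5 cut points.

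The cost is mainly text, because TLFB and CAS are already collected at baseline. Aligning the CAS windows could also mean changing how the CAS is administered; the alternative above avoids that. The small downside is that some women will have a baseline count of 0 and leave the resolution classification.

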The sample size of no more than 155 women would also be sufficient for detecting changes in the proportion of women indicating an alcohol use problem or occurrence of IPV over the follow-up. Based on findings suggesting that 7-14% of VA women with MST report SUD, and 64% of women with any lifetime sexual abuse report alcohol abuse, we conservatively estimate that 40% of women included in the study will screen positive for alcohol problems. Thus, the sample of no more than 155 accounting for attrition would allow a power of .80 to detect an effect size  $h$  of .44 of changes in alcohol use problems over the follow-up. This would be achieved with rates of alcohol use problems of 20% vs. 40% in control. Further, based on data indicating that 33% of women with a history of sexual victimization are revictimized, 44% of active duty military women report lifetime IPV, and studies indicating that IPV revictimization ranges from 18% to 74% over 6- to 9-month follow-ups (see Kuijpers et al., 2011), we conservatively estimate that 40% of women with a history of lifetime ST presenting at the VA would report lifetime IPV, and 25% would report a revictimization experience over the 4-month follow-up. A sample of no more than 155 accounting for attrition would allow a power of .80 to detect an effect size  $h$  of .46 in changes in IPV revictimization over the 4-month follow-up. This would be achieved with rates of IPV revictimization of 8.5% in the SHE program vs. 25% in the control group.

The sample size of no more than 155 will also be sufficient for detecting changes in the proportion of women who reduce the number of risks over the follow-up. Among the full sample of no more than 155 women, power would be .85 to detect an effect size  $h$  of .44 in any reduction (i.e., 1 to 0 risks, 2 to 1 risk, 3 to 2 risks, etc.) in the number of risks; which would be achieved, for example, with 20% of women in control and 40% of women in SHE reducing the number of risks reported over the follow-up. Power would also be adequate to examine reductions in the number of risks among women experiencing various numbers of risks (i.e., women reporting 1 risk vs. 2. vs. 3). In light of high comorbidity between PTSD, IPV, and

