substance use, we projected that 50 women will report 1 risk, 50 women will report 2 risks, and 50 women will report three risks. Thus, among women reporting each number of risks (i.e., we expect 50 women will report 1 risk), power would be .73 to detect an effect size  $h$  of .64, which would be achieved with 20% of women in the control group reporting a reduction, and 50% of women in SHE reporting a reduction.

**Limitations** The limitations of this study include: potential issues related to disclosure of sensitive information, the use of self-report, assessment reactivity and effect on measured outcomes, the inclusion of only English-speaking participants, generalizability of study results to other Veteran or service member populations, and an inability to meaningfully examine ethnic/racial differences in the proposed sample.

**Revision:** Based upon experience during the Development and Trial Phase, evaluation of the program, and feedback from participants, the Investigator Team will revise the intervention. Information regarding the recruitment methods and retention of participants will be utilized in the design of a later clinical trial. This final revision phase will generate the final “product” of this treatment development study, to be used in the application to evaluate SHE in a large-scale clinical trial.

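### The all-versus-some resolution contrast is confined to women who improved after randomization, so a real SHE benefit can show up as apparent harm

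*Combined protocol and SAP*

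**What the plan says.** The relevant text is in the combined protocol and SAP, Data Analysis, under Primary outcomes (Aim 4a). The main analysis is a Poisson GEE of the number of risks at 2 and 4 months, with the baseline number of risks as covariate. On the analysis population the plan says that "all women who completed the baseline assessment and who are randomized will be included in the analyses".

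A second step follows: "To further illustrate program effects, each of the participants will then be classified over the follow-up". The classes are "1) resolving all risks; 2) resolving some but not all risks; and 3) resolving no risks or increasing the number of risks". Two contrasts between arms are planned:

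- All versus none/increased: "Intervention effectiveness will be measured by comparing the proportion of women resolving all risks, to the proportion of women resolving no risks or increasing risks", compared between the groups.
- All versus some: "The proportion of women resolving all risks will also be compared to the proportion of women resolving some risks between groups".

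For neither contrast does the plan state a denominator, a model or how the baseline number of risks is handled.

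The Power Analysis adds two relevant figures. For any reduction in the number of risks it works "with 20% of women in control and 40% of women in SHE reducing the number of risks reported over the follow-up". For the baseline mix it says "we projected that 50 women will report 1 risk, 50 women will report 2 risks, and 50 women will report three risks".

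**The concern.** The three classes are ordered from best to worst, but each contrast uses only two of them. The loss matters differently in the two cases.

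All versus none/increased ignores the middle class but compares the two ends of the scale. All versus some compares two grades of success among women who have already improved. Membership of that group is itself an outcome of treatment. If SHE moves women from no improvement to partial improvement, they enter the contrast on its unfavourable side, and SHE looks worse for having helped them.

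The baseline number of risks adds a structural problem. A woman with one risk either resolves it or does not, so she can never be in the middle class. She appears in all versus some only if she succeeds.

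The stake is the estimate. The Power Analysis section makes a reasonable effect size for planning a later trial the primary objective. A contrast whose sign depends on how partial improvement is distributed cannot supply one.

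**Working it through.** **Inputs from the documents** (Power Analysis, except the last)
- Any reduction in risks: 20% control, 40% SHE.
- Enrolled: at most 155. Retained: 126.
- Projected baseline mix: 50, 50 and 50 women with one, two and three risks.
- Within-stratum example: 20% control versus 50% SHE reducing.
- Equal allocation, so 126/2 = 63 retained per arm (the Potential Benefits section says that half receive no intervention).

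**Assumption.** The documents do not divide women who improve into all and some. Control is taken as 10% all and 10% some, and the SHE split is varied with any reduction fixed at 40%.

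**The plan's own figure.** Power for any reduction is stated as .85. Cohen's h for 20% versus 40% is 0.442. With 77.5 women per arm, h × √(77.5/2) = 2.75. One-sided alpha .05 gives power 0.87 (0.86 at N = 150); two-sided gives 0.79. The figure is therefore reproduced closely with a one-sided test; the plan does not state sidedness. This power refers to all and some together versus none, which is neither of the two planned contrasts.

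**Illustration.** Control 10/10/80 and SHE 15/25/60 (all/some/none, in percent). SHE is better at both cuts: all 15% versus 10%, any reduction 40% versus 20%.

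- All versus none: OR = (0.15/0.60)/(0.10/0.80) = 0.250/0.125 = 2.0, favouring SHE.
- All versus some: control 0.10/0.20 = 50%, SHE 0.15/0.40 = 37.5%; OR = (0.15/0.25)/(0.10/0.10) = 0.60, apparent harm.
- Women in all versus some: 63 × 0.20 = 12.6 control and 63 × 0.40 = 25.2 SHE.

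This split is what one plausible pattern produces. Take the 50/50/50 mix and let a quarter of improving women with two or three risks resolve all of them. Leave one-risk women at 20% in both arms, and let the others go from 20% to 50%. Control all = (20 + 5 + 5)/3 = 10%. SHE all = (20 + 12.5 + 12.5)/3 = 15%, and SHE some = (0 + 37.5 + 37.5)/3 = 25%.

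**Range over the unstated split** (control fixed at 10/10/80)

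| SHE all | SHE some | OR, all vs none | OR, all vs some |
|---|---|---|---|
| 10% | 30% | 1.33 | 0.33 |
| 12% | 28% | 1.60 | 0.43 |
| 15% | 25% | 2.00 | 0.60 |
| 18% | 22% | 2.40 | 0.82 |
| 20% | 20% | 2.67 | 1.00 |
| 25% | 15% | 3.33 | 1.67 |
| 30% | 10% | 4.00 | 3.00 |

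All versus some points to harm whenever SHE's all rate is below twice control's, although any reduction has doubled.

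**Other patterns on the 50/50/50 mix.** A uniform doubling in every stratum gives an all-versus-some OR of 1.00, so the benefit is invisible. If each risk resolves independently at a common rate, the OR is 1.26 (10% to 20% per risk) to 1.68 (20% to 40%), the right direction.

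**Direction of all versus none.** If SHE raises the all proportion and lowers the none proportion, the ratio all/none must rise, so this contrast cannot reverse under such an improvement.

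**One-risk women.** 50/150 = 33.3% of the projected sample cannot be in the middle class.

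**The case against.** Much can be said for the plan. The classification is introduced as an illustration, after a GEE that uses all women and carries the baseline number of risks. The sentence about measuring effectiveness attaches to all versus none/increased, which keeps its direction; all versus some is an added comparison. Both would be reported, and in the illustration they jointly imply a some-versus-none OR of 2.0/0.60 = 3.3 for SHE, so a careful reader of the full output would not conclude harm. Urn randomization and the balance check on number of risks should spread one-risk women evenly, and the Power Analysis section envisages looking at women with one, two and three risks separately. All of this stands, and it lowers the severity.

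It does not repair all versus some. A multinomial model with all as reference would keep every classified woman, but its unadjusted odds ratio is the same 0.60. Using full denominators does not help either: all minus some is 10 − 10 = 0 points in control and 15 − 25 = −10 points in SHE. Balance between arms does not create a middle class for one-risk women.

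A reader might infer that the step breaks the intention-to-treat commitment. The documents do not support that: they say each participant is classified and leave denominator and model unstated. Leaving women out is the natural reading of a two-class contrast, but not a stated rule.

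**Conclusion.** The point holds for all versus some. That contrast can give the wrong sign for a real benefit: OR 0.60 where all versus none gives 2.0, on about 38 of 126 retained women. Its value ranges from 0.33 to 3.0 over SHE splits compatible with the plan's 20% versus 40%. The range rests on an assumed control split of 10/10, since the documents give none.

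Two stronger conclusions may suggest themselves and are not supported. One is that both contrasts can reverse: all versus none/increased discards the middle class but keeps the right direction when SHE raises all and lowers none. The other is that reversal is to be expected: under some patterns all versus some is null or correct.

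That one-risk women cannot be in the middle class follows from the class definitions; their share, one third, is the plan's projection. The main Aim 4a GEE is unaffected. Severity is moderate to low.

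**What to change.** Replace the two pairwise contrasts with one comparison of the three ordered classes that keeps every classified woman and accounts for baseline number of risks. Use either a row-mean-score test stratified by baseline number of risks or a proportional-odds model adjusted for it. Stratification compares one-risk women only with each other, so their empty middle class does no damage.

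Also report, by arm, the proportion in each class, and the arm difference in the proportion resolving all risks with a 95% CI. Take all randomized women with follow-up as the denominator, in line with the commitment under Data checking to use all available data. Add a sensitivity analysis that counts women without follow-up (155 − 126 = 29 on the plan's projection) as not resolved. State which follow-up visit defines the class.

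The cost is a revised paragraph and a little more analysis; no new data are needed. The proportional-odds model brings its own assumption, which the reported class proportions let readers check.
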